## List of Abbreviations

Abbreviation or Specialized Term	Definition
ADA	anti-drug antibody
AE	adverse event
ALT	alanine aminotransferase
AST	aspartate aminotransferase
ATC	Anatomical Therapeutic Chemical
BL	baseline
CI	confidence interval
CR	complete response
CRC	colorectal cancer
DA	disease assessment
DC	disease control
DCR	disease control rate
DLT	dose-limiting toxicity
DoR	duration of response
ECG	electrocardiogram
ECOG	Eastern Cooperative Oncology Group
CCI	CCI
CCI	CCI
CCI	CCI
ILD	Interstitial Lung Disease
CCI	CCI
IP	investigational product
CCI	CCI
CCI	CCI
CCI	CCI
CCI	CCI
IV	Intravenous
IXRS	interactive voice/web response system
MedDRA	Medical Dictionary for Regulatory Activities
MTD	maximum tolerated dose
NCI CTCAE	National Cancer Institute Common Terminology Criteria for Adverse Events
NE	not evaluable
OR	objective response
ORR	objective response rate
OS	overall survival
PD	progressive disease
PFS	progression-free survival
PK	pharmacokinetic(s)

Abbreviation or Specialized Term	Definition
PR	partial response
RP2D	recommended Phase 2 dose
RECIST	Response Evaluation Criteria in Solid Tumors
SAE	serious adverse event
SD	stable disease
SPP	statistical programming plan
TEAE	treatment-emergent adverse event
TSH	thyroid stimulating hormone
ULN	upper limit of normal

## 1 INTRODUCTION

This document describes the statistical analysis methodology for protocol D6070C00004, a multiarm, open-label, multicenter, phase 1b/2 study to evaluate novel combination therapies in subjects with previously treated advanced EGFRm NSCLC. As background information, an overview of the study design is provided. The main portion of this document details the statistical summaries relating to each study objective and describes the general conventions and definitions that will be used. In addition, a set of table templates and specifications will be included in a statistical programming plan (SPP) to complement this document.

## 2 STUDY OVERVIEW

### 2.1 Study Objectives

#### 2.1.1 Primary Study Objective(s)

Part 1:

- To investigate the safety and tolerability of novel combination therapies administered in subjects with advanced EGFRm NSCLC and confirm the combination dose(s) for further clinical evaluation

Part 2:

- To investigate the antitumor activity of novel combination therapies administered in subjects with advanced EGFRm NSCLC by evaluation of tumor response based on Response Evaluation Criteria in Solid Tumors (RECIST) version 1.1
- To investigate the safety and tolerability of novel combination therapies administered in subjects with advanced EGFRm NSCLC

#### 2.1.2 Secondary Study Objectives

Parts 1 and 2

1. To obtain a preliminary assessment of the antitumor activity of novel combination therapies administered in subjects with advanced EGFRm NSCLC by evaluation of tumor response based on RECIST version 1.1
2. To evaluate the antitumor activity of novel combination therapies administered in subjects with advanced EGFRm NSCLC based upon T790M testing at baseline confirmed by a central lab
3. To determine the pharmacokinetic (PK) profile of individual analytes of novel combination therapies (oleclumab with investigational name MEDI9447, osimertinib, and AZD4635) administered in subjects with advanced EGFRm NSCLC
4. To determine the immunogenicity of oleclumab administered in subjects with advanced EGFRm NSCLC

### 2.1.3 Exploratory Study Objectives

CCI

## 2.2 Study Design

[figure not shown]
This is a multiarm, open-label, multicenter, Phase 1b/2 study to evaluate novel combination therapies in subjects with previously treated advanced EGFRm NSCLC. The study is divided into 2 parts. In Part 1 the safety and tolerability of novel combination therapies will be evaluated and a RP2D for combination therapy will be identified. In Part 2 the safety, tolerability, and preliminary antitumor activity of novel combination therapies will be evaluated. Subjects will be treated in Arm A (oleclumab and osimertinib combination therapy) or Arm B (oleclumab and AZD4635 combination therapy). The allocation of subjects to treatment arms will be dependent upon the subject's EGFR mutation status and prior therapies. Additional treatment arms may be added as part of this multidrug protocol as decisions on the most appropriate combinations to use become available and as the scientific understanding of EGFRm NSCLC develops. A substantial protocol amendment with relevant nonclinical and clinical data will be put in place before starting a new combination treatment arm.

A total of up to approximately 98 subjects will be enrolled in this study at approximately 15 sites globally: up to approximately 46 subjects in Arm A and up to approximately 52 subjects in Arm B.

During Part 2 dose expansion, Bayesian predictive probabilities will be used for continuous interim monitoring analysis for efficacy and safety. Subjects dosed at the RP2D in Part 1 will be included in this analysis (Protocol Section 4.8.8).

The study flow is presented in [Figure 2.1.3-1](#) for Part 1 and in [Figure 2.1.3-2](#) for Part 2.

[figure not shown]
**Figure 2.1.3-1 Study Flow Diagram for Part 1: Dose Escalation**

EGFRm = epidermal growth factor receptor mutant; EGFR TKI = epidermal growth factor receptor tyrosine kinase inhibitor; IV = intravenously; N = number; NSCLC = non-small cell lung cancer; PO = orally; Q2W = every 2 weeks; QD = once daily.

**NOTE:** For both Arms A and Arm B, subjects must have received treatment with an approved first or second generation EGFR TKI except for subjects in Arm B who received osimertinib as first-line treatment, in which case, treatment with a first or second generation EGFR TKI is not required, and these subjects may enroll after having received and progressed on osimertinib alone (but can still have received no more than 4 prior lines of therapy).

**Figure 2.1.3-2 Study Flow Diagram for Part 2: Dose Expansion**

EGFRm = epidermal growth factor receptor mutant; EGFR TKI = epidermal growth factor receptor tyrosine kinase inhibitor; IV = intravenously; N = number; NSCLC = non-small cell lung cancer; PO = orally; Q2W = every 2 weeks; QD = once daily; RP2D = recommended Phase 2 dose.

**NOTE:** For both Arms A and Arm B, subjects must have received treatment with an approved first or second generation EGFR TKI except for subjects in Arm B who received osimertinib as first-line treatment, in which case, treatment with a first or second generation EGFR TKI is not required, and these subjects may enroll after having received and progressed on osimertinib alone (but can still have received no more than 4 prior lines of therapy).

Response-evaluable subjects are subjects who receive any investigational product, had measurable disease at baseline and at least 1 post-baseline tumor assessment, or who died from any cause or who discontinued due to clinical progressive disease prior to any post-baseline tumor assessment.

a Including subjects dosed at the RP2D in Part 1

- b Arm A: Continuous interim monitoring will begin after 10 subjects are response-evaluable (including subjects dosed at the RP2D in Part 1).
- c Arm B: Continuous interim monitoring will begin after 20 subjects are response-evaluable (including subjects dosed at the RP2D in Part 1).

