## 3.2 Analysis Populations

**Table 3.2-1 Analysis Populations**

Population	Description
As-treated population	The As-treated population includes subjects who receive any study investigational product. Subjects will be analyzed according to the treatment they actually receive. All analyses will be performed on the As-treated Population unless otherwise specified.
Response-evaluable population	The Response-evaluable population includes subjects from the As-treated Population who have a baseline disease assessment (DA), have the opportunity to be followed for at least 8 weeks at the time of the data cutoff (ie, dosed at least 8 weeks prior to the time of the data cutoff), and either has at least one post-baseline DA and/or discontinued treatment due to death or disease progression.
DLT evaluable population	The DLT evaluable Population includes subjects enrolled in the dose-escalation phase who receive all planned doses of oleclumab and at least 75% of the daily administrations of osimertinib (Arm A) or AZD4635 (Arm B) during the DLT-evaluation period (defined as from the first dose of both investigational products until the planned administration of the third dose of oleclumab; this corresponding to Day 28 post Dose 1 of oleclumab) and complete the safety follow-up through the DLT-evaluation period or experience any DLTs.

The number and percent of subjects in each subject population for evaluation will be summarized.

Unless stated otherwise, subject disposition and baseline characteristics, exposure to each investigational product (IP), safety analyses, and efficacy analyses will be based on as-treated population; DLT-evaluable population will be used for the RP2D evaluation.

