## **3.4 Efficacy Analyses**

### **3.4.1 Primary Efficacy Endpoint(s) and Analyses**

#### **3.4.1.1 Primary Efficacy Endpoint(s) and Analysis**

The primary efficacy endpoint is objective response per RECIST 1.1 by investigator assessment. Objective response rate (ORR) is defined as the proportion of subjects with a best overall response of confirmed CR or confirmed PR that occur prior to the initiation of

subsequent anticancer treatment. The rules for confirmation of CR or PR are the same as described in Section 3.4.2.1. The primary analysis of ORR will be based on the as-treated population in Part 2 (including subjects dosed at the RP2D in Part 1). ORR will be estimated with a 95% CI using the exact binomial distribution. Subjects that have missing best overall response assessments will be considered non-responders, and will therefore be counted in the denominator, but not in the numerator of ORR. In addition, above analysis may also be performed based on the response -evaluable population in Part 2 (including subjects dosed at the RP2D in Part 1).

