## 4 INTERIM ANALYSIS

The interim analyses will be performed separately for each dose-expansion cohort (Arm A and Arm B) starting at 10 response-evaluable subjects for Arm A and 20 response-evaluable subjects for Arm B (including subjects dosed at the RP2D in Part 1). Enrollment may be paused at the initial interim analysis for each arm to allow full analysis of results. If the No-Go criteria are NOT met, enrollment may continue. After the initial interim analysis, the subsequent interim analyses will be performed after every 5 additional subjects are response-evaluable. If futility decision is made at an interim analysis, the enrollment will be terminated. An efficacy analysis may also be performed at each interim analysis. The results of the efficacy analysis will not impact on the stopping rule but may trigger other planning activities for further development of oleclumab combinations.

Continuous monitoring based on Bayesian predictive probability will be used for the interim analyses (Lee and Liu, 2008). In this study, for dose expansion cohorts Arm A and B, different ORRs were assumed as the target response rates for decision making. CCI

CCI

CCI

CCI

The interim analyses will be based on the Response-evaluable Population as defined in Section 3.2.

CCI

CCI

[figure not shown]

To assess the operating characteristics of this continuous interim monitoring method, overall go or no-go probabilities, average sample sizes to achieve the decisions, and probabilities of making early decisions were calculated based on 10000 simulations and assumed true response rates (CCI [REDACTED]). Decision consistencies (or accordance) between a design using continuously monitoring and a design without interim monitoring were also compared. The results are shown in [Table](#) for Arm A and [Table](#) for Arm B.

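### Response-evaluable is defined in two non-equivalent ways, and the governing Table 3.2-1 leaves out of the Go/No-Go set subjects who stop treatment for another reason and die before any scan

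*SAP*

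**What the plan says.** **Figure 2.1.3-2 notes (SAP Section 2.2).** Response-evaluable subjects received any investigational product and "had measurable disease at baseline and at least 1 post-baseline tumor assessment, or who died from any cause", or are subjects "who discontinued due to clinical progressive disease prior to any post-baseline tumor assessment". No minimum time since dosing is required. Notes b and c, below this definition, start continuous monitoring at 10 response-evaluable subjects in Arm A and 20 in Arm B.

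**Table 3.2-1 (SAP Section 3.2).** The population is "subjects from the As-treated Population who have a baseline disease assessment (DA), have the opportunity to be followed for at least 8 weeks" at the data cutoff, where the subject "either has at least one post-baseline DA and/or discontinued treatment due to death or disease progression". Measurable disease is not mentioned.

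**SAP Section 4.** Looks are planned "starting at 10 response-evaluable subjects for Arm A and 20 response-evaluable subjects for Arm B" and then "after every 5 additional subjects are response-evaluable". A futility decision ends enrollment in the arm. On the analysis set: "The interim analyses will be based on the Response-evaluable Population as defined in Section 3.2".

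**SAP Section 3.4.1.1.** "The primary analysis of ORR will be based on the as-treated population in Part 2", including Part 1 subjects dosed at the RP2D. A subject with no best overall response stays in the denominator as a non-responder.

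**The concern.** One term with two meanings is attached to the same 10- and 20-subject milestones. Section 4 settles which text the interim analysis uses, but the figure still places a different definition just above the triggers. Whoever counts subjects towards a look from the figure can reach a different number from whoever builds the dataset from Section 3.2.

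Choosing Table 3.2-1 does not remove the difficulty, because its last condition depends on the reason for stopping treatment and not on what happened to the subject. A death before any scan counts only when death or progression was the reason treatment ended. A subject who had already stopped for something else, and then died, drops out of the set that decides futility. That subject is a certain non-responder, so the omission can only raise the interim ORR.

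At stake is the interim futility decision, together with the optional response-evaluable summaries. The trial is open-label, so the denominator should be fixed before responses are known.

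**Working it through.** **1. The plan's own figure.** The one readable operating characteristic tied to this rule is in SAP Section 4: an 8% chance of a no-go in Arm A when the true response rate is 0.4. It cannot be reproduced, because the target rates and predictive-probability cut-offs are redacted. That is not a fault in the plan, but it means the effect of the definition on the decision cannot be calculated.

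**2. The definitions side by side.**

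| Subject | Figure 2.1.3-2 note | Table 3.2-1 | As-treated primary ORR |
|---|---|---|---|
| A. Stops for an AE or by decision, then dies before any scan | In | Out | In, non-responder |
| B. Non-target disease only at baseline, scanned, dosed at least 8 weeks before cutoff | Out | In | In |
| C. Death or clinical progression before any scan, dosed less than 8 weeks before cutoff | In at once | Not yet | In |
| D. Scanned early, dosed less than 8 weeks before cutoff | In, if disease measurable | Not yet | In |

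Row A is possible under the SAP's own categories: Section 3.3.1 lists adverse event, subject decision and investigator decision as reasons for ending treatment, separate from death and progressive disease. Section 3.4.2.1 classes an early death without adequate data as non-evaluable but keeps it in the denominator of response rates.

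For row B, Appendix 7.1.1 sets target lesion response to NA when there are no target lesions at baseline. In the Appendix 7.1.3 table, an NA target response leads to CR, SD (Non-CR/Non-PD), NE or PD. No NA row gives PR.

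Rows A, C and D affect when the 10th or 20th subject is reached under the two texts, and row B does so if such subjects exist. Rows A and B change who is in the interim ORR.

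**3. Size of row A at one cutoff.** Let x be the responders and n the counted subjects. Restoring one omitted death changes the ORR from x/n to x/(n+1), a fall of x/[n(n+1)]. The counts below are illustrative.

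- Arm A, n = 10, x = 4: 4/10 = 40.0% against 4/11 = 36.4%, a difference of 3.6 points.
- Arm A, n = 10, x = 3: 3/10 = 30.0% against 3/11 = 27.3%, 2.7 points.
- Arm B, n = 20, x = 4: 4/20 = 20.0% against 4/21 = 19.0%, 1.0 point.

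**4. Size of row A when the look is triggered by count.** Looks occur at a fixed number of evaluable subjects, so an omitted death is replaced by the next subject to qualify. If that subject responds with probability p, the omission raises the expected ORR by p/n. With p = 0.4 (the plan's illustrative rate for Arm A) and n = 10, this is 0.4/10 = 4.0 points per omitted death. At n = 20 it is p/20, and the plan shows no readable p for Arm B.

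**The case against.** The strongest reply is that the SAP already says which text governs. Section 1 calls the study overview background, the figure note belongs to that overview, and Section 4 repeats the triggers and points to Section 3.2. This stands. The figure note is a leftover that conflicts with a named definition, and the analysis set itself is not open.

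It follows that one tempting inference fails. A reader might conclude that the interim ORR is biased downward because early deaths and progressions enter at once while ongoing subjects wait for a scan. A simulation with assumed inputs (true ORR 0.40, 10–20% early failures before week 8, 2–4 subjects per month) does give a mean ORR of 0.37–0.39 among the first 10 evaluable subjects. But that arises only under the figure note. The 8-week rule in Table 3.2-1 is what prevents it.

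The target-lesion point is conditional. Eligibility is in the protocol, which is not shown, and the NA rows in the appendix do not prove that such subjects can enrol. Nor are they certain non-responders, since NA with a non-target CR yields CR.

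Row A is narrow: it needs treatment stopped for another reason, then death, with no scan in between, and the SAP gives no frequency. The gap in the wording remains.

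Finally, monitoring on evaluable subjects while judging the final ORR on as-treated subjects is a stated design choice. The difference between those two sets is not in itself an error.

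**Conclusion.** The contradiction between the two definitions is real, and the governing Table 3.2-1 has a defect of its own: deaths before any scan are omitted when treatment had already stopped for a reason other than death or progression. The direction is upward for the interim ORR. The size is about 3 to 4 points per omitted subject at the first Arm A look and about 1 point at the first Arm B look, on the assumed responder counts shown. If subjects without target lesions can enrol, their inclusion would tend to pull the other way, because only CR is open to them.

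Two larger claims are not supported. A shift of 10 points from one subject needs an extreme case, such as 9/10 = 90% becoming 9/9 = 100%. And a material change in the no-go probability might be inferred, but any figure for it would rest on invented cut-offs and an invented share of affected subjects. The primary ORR is unaffected, because it uses the as-treated population and counts missing responses as failures.

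**What to change.** - Keep Table 3.2-1 as the single definition, with its 8-week opportunity rule.
- Reword its last condition so that a subject qualifies with one or more disease assessments after baseline or, failing any, with death from whatever cause or progression (radiological or clinical) before the first such assessment. The reason for stopping treatment then no longer matters.
- State in Table 3.2-1 whether measurable disease at baseline is required, consistent with the protocol's eligibility criteria.
- Replace the definition in the Figure 2.1.3-2 notes with a cross-reference to Section 3.2, so that notes b and c and Section 4 count the same subjects.

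The cost is SAP wording only; the 10, 20 and every-5 triggers stay as they are. The interim ORR may come out slightly less favourable, because the omitted early deaths are now counted.

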## 2.3 Treatment Assignment and Blinding

### Treatment Assignment

An interactive voice/web response system (IXRS) will be used for assignment of unblinded investigational product kit numbers to each subject who meets the eligibility criteria. A subject is considered entered into the study when the investigator notifies the IXRS that the subject meets eligibility criteria and the IXRS provides the assignment of unblinded investigational product kit numbers to the subject.

Oleclumab must be administered within 1 business day after the investigational product is assigned. If there is a delay in the administration of oleclumab such that it will not be administered within the specified timeframe, the study monitor must be notified immediately.

### Blinding

The study is not blinded.

## 2.4 Sample Size

A total of up to approximately 98 subjects will be enrolled in this study, up to approximately 46 subjects in Arm A and up to approximately 52 subjects in Arm B.

CCI  
[Redacted]

CCI  
[Redacted]

CCI  
[Redacted]

**Table 2.1.3-1** CCI [Redacted]

CCI [Redacted]

### 3 STATISTICAL METHODS

#### 3.1 General Considerations

Tabular summaries will be presented by treatment group. Categorical data will be summarized by frequency distribution (number and percentage of subjects falling within each category). Continuous variables will be summarized by descriptive statistics including N, mean, standard deviation, median, and range (minimum and maximum). All available data will be used and thus missing data will not be imputed. In general, subjects with missing data for a parameter will be excluded from the summary of this parameter. Tables will be supported by data listings showing the original data forming the basis for the summaries. Data listings will be sorted by treatment group, subject number and date collected where applicable.

In general, unless stated otherwise, two-sided confidence intervals will be produced at 95%. Baseline values will be defined as the last valid assessment prior to the first administration of investigational product.

The data analyses will be conducted using the SAS® System (SAS Institute, Inc., Cary, NC, USA) Version 9.3 or above. All analysis outputs will be validated according to MedImmune SAS programming standards and MedImmune validation procedures.

## 3.2 Analysis Populations

**Table 3.2-1 Analysis Populations**

Population	Description
As-treated population	The As-treated population includes subjects who receive any study investigational product. Subjects will be analyzed according to the treatment they actually receive. All analyses will be performed on the As-treated Population unless otherwise specified.
Response-evaluable population	The Response-evaluable population includes subjects from the As-treated Population who have a baseline disease assessment (DA), have the opportunity to be followed for at least 8 weeks at the time of the data cutoff (ie, dosed at least 8 weeks prior to the time of the data cutoff), and either has at least one post-baseline DA and/or discontinued treatment due to death or disease progression.
DLT evaluable population	The DLT evaluable Population includes subjects enrolled in the dose-escalation phase who receive all planned doses of oleclumab and at least 75% of the daily administrations of osimertinib (Arm A) or AZD4635 (Arm B) during the DLT-evaluation period (defined as from the first dose of both investigational products until the planned administration of the third dose of oleclumab; this corresponding to Day 28 post Dose 1 of oleclumab) and complete the safety follow-up through the DLT-evaluation period or experience any DLTs.

The number and percent of subjects in each subject population for evaluation will be summarized.

Unless stated otherwise, subject disposition and baseline characteristics, exposure to each investigational product (IP), safety analyses, and efficacy analyses will be based on as-treated population; DLT-evaluable population will be used for the RP2D evaluation.

